1. PURPOSE OF THE STUDY AND BACKGROUND

1.1: Purpose of the Study:

Inactivated influenza vaccine (“IIV”) is an intramuscular vaccine administered to children ≥ 6 months in age that is composed of highly purified HA and NA surface glycoproteins and contains trace, if any, activators of the immune system. In contrast, live attenuated vaccine (“LAIV”) consists of intranasally delivered, attenuated viruses that stimulate the innate immune system while undergoing limited viral replication in the upper respiratory tract. Some children also continue to first encounter influenza through natural infection, where high levels of viral replication stimulate vigorous innate immunity. Although CD4 T cells play a key role in regulating the influenza-specific B cell, CD8 T cell, and innate immune responses, little is known about the immediate and long-term effects these different routes of early childhood priming have on CD4 T cell mediated immunity. The long-term goal of this research is to understand how a child’s early exposure to influenza shapes immunity and poises the immune system to respond to subsequent influenza challenge. Our objective is to determine how the anti-influenza CD4 T cell and antibody responses are altered by the mode of primary influenza encounter and establish the consequences this has on subsequent influenza vaccination. To accomplish this objective, we will enroll two cohorts of young children: 1) a cohort of 24 through 35 month of children administered either LAIV or IIV and 2) a separate cohort of infants first exposed to influenza through prime-boost administration of IIV or natural infection during their initial influenza season. All enrolled subjects will be followed longitudinally to the subsequent influenza season and then rechallenged with IIV. These cohorts of children will allow us to test the following hypotheses:

- 1) Compared to intramuscular IIV, initial exposure to intranasal LAIV establishes a greater and more polyfunctional CD4 T cell response in children 24 through 35 months of age
- 2) Compared to a first exposure to influenza through infection, primary infant vaccination with IIV establishes a more limited CD4 T cell repertoire that consists predominately of IL-2 producing cells, and
- 3) The CD4 T cell responses established with this initial priming will differentially poise subjects to respond to revaccination with IIV the following influenza season

Completion of this research will determine the effect of different methods of priming on the specificity and functional potential of the anti-influenza CD4 T cell and antibody responses. These experiments will fill a critical void in our understanding of the primary human immune response to influenza and generate knowledge enabling the rational development of novel influenza vaccines.

The specific objectives for this study include the following:

- To comprehensively evaluate the specificity and functional potential of CD4 T cell responses using intracellular cytokine staining and Elispot assays following restimulation with pools of HA and NP peptides
- To assess the full spectrum of antigen-specific CD4 T cell cytokine and chemokine production using multiplex cytokine assays
- To evaluate the humoral immune response that develops in response to infection or administration of LAIV or IIV vaccines
- To evaluate the memory B cell response established by different routes of exposure to influenza
- To determine the influence of the CD4 T cell response on the breadth and avidity of the post-vaccination antibody response using arrayed imaging reflectometry to rapidly quantify antibody levels against multiple HA proteins, microneutralization assays to quantify neutralizing antibody titers against different viral strains, and enzyme linked immunosorbent assays to determine HA antibody avidity and quantify stalk reactive antibody
- To evaluate in an unbiased way the influence of previous influenza exposure on PBMC gene expression patterns using RNA-seq analysis
- To assess the mucosal immunity established by these modes of priming and determine whether any initially established differences in mucosal immunity are maintained on subsequent challenge with IIV

1.2: Background:

Influenza is a virus in the family *Orthomyxoviridae* that infects the host respiratory tract mucosa and causes a contagious acute respiratory infection (1). This virus contains a genome composed of eight strands of

negative-sense RNA that encode viral proteins (2). Vaccines against this virus have traditionally relied on inducing antibodies that protect against viral infection by binding to the HA surface glycoprotein and neutralizing virions. However, the rapid accumulation of point mutations in both the HA and NA proteins allow this virus to drift and escape neutralization, resulting in yearly epidemics despite the availability of influenza vaccines (1, 3). In addition, the segmented genome of influenza virus allows sporadic reassortment to occur, which can result in antigenic shift and creation of a strain against which the population has little preexisting immunity. Such a reassortment event occurred in 2009, when a novel swine-origin influenza virus emerged and spread globally, resulting in the first influenza pandemic of the 21st century (4, 5).

It is estimated that 20% of children become infected with influenza yearly, with increasing rates during severe epidemics (6, 7). In addition to providing a reservoir for community infection, childhood influenza infection results in a substantial number of outpatient and emergency room visits and can be associated with significant morbidity, including viral or secondary bacterial pneumonia (6-8). Hospitalization is highest in the very young (estimated at 4.5 per 1000 children 0 to 5 months old) (8), with overall childhood influenza-related mortality estimated at 0.21 deaths per 100,000 children (9). While annual influenza immunization is the most effective method to prevent infection, the influenza vaccine is suboptimal in children (10-12). Some evidence suggests that LAIV may induce broader, more protective immunity in the young (11, 13-16), however recently presented data demonstrated that LAIV failed to protect against H1N1 strains in the 2013-14 influenza season. Further, LAIV is not yet approved for use under the age of 2 due to concerns about the precipitation of wheezing (17, 18). As IIV is universally recommended in the USA beginning at 6 months of age (18, 19), increasing numbers of children are first exposed to influenza via IIV.

Major strides in understanding the protective immune response to influenza have been made in recent years. Natural influenza infection stimulates vigorous inflammation with activation of multiple pattern recognition receptors. This leads to a robust innate immune response characterized by production of antiviral cytokines such as interferons that both limit early viral replication and instruct developing adaptive immunity (1, 20-23). As the infection progresses, viral replication results in abundant intracellular antigen that can be processed and presented to activate the adaptive immune response (1, 23). CD4 T cells have a multifaceted role in combating infection, providing help to promote B cell isotype switching and affinity maturation, CD8 T cell memory generation, and directly participating in viral clearance through the independent secretion of antiviral cytokines and direct, cell-mediated cytotoxicity (1, 3, 23-33). Additionally, CD8 T cells are activated and home to respiratory sites to eliminate infected cells (1, 3, 23, 28, 29) and antigen-specific B cells secrete high affinity, neutralizing antibodies that are able to provide strain-specific sterilizing immunity from future infection (1, 23, 34-37). While neutralizing antibody is thought of as the major correlate of protection (34-37), cellular immunity is increasingly recognized as important in protecting from severe disease (38-41). As T cells can recognize epitopes from conserved internal viral proteins (42-46), this protection can be very important in years when antigenic drift leads to a poor vaccine match or a pandemic influenza strain emerges.

In contrast to the robust response that develops following influenza infection, the immune response generated on vaccination with IIV is characterized by weak inflammatory signaling. These vaccines are produced by chemical inactivation of the H1N1, H3N2, and influenza B viral strains predicted to be circulating, with disruption and purification of the surface glycoproteins (HA and NA) (47-49). Vaccine is solely quantified based on the content of the HA protein and generally contains variable levels of NA, small amounts of internal virion proteins including NP, and only trace amounts of innate immune activators such as viral RNA (47, 50-52). This vaccine is delivered intramuscularly without the addition of an adjuvant in the USA (50-52). While IIV stimulates antibody (53-59) and CD4 T cell responses (59-63), little CD8 T cell immunity

[figure not shown]

Figure 1: Preexisting immunity can have a profound effect on both CD4 T cell and antibody responses. Mice were initially infected with an H3 influenza virus, followed by challenge with an H1 strain 9 weeks later. (A) Splenocytes were enriched for CD4 T cells by MACS purification and incubated with known peptide-epitopes along with syngeneic splenocytes from uninfected animals as APC. Compared to following a primary infection (open squares), HA-specific CD4 T cell responses were suppressed following secondary infection (black circles). Asterisks denote a P-value <0.05 by Student's t test. (B) Sera obtained from mice following primary or secondary infection was tested for HA-specific antibody by ELISA. H1 HA-specific antibody was suppressed following secondary challenge with an H1 virus (black circles) compared to the primary infection (open squares). Triangles represent serum antibody from H3 infected animals (upwards) or naïve serum (downwards). Error bars represent the standard error of the mean.

is generated due to limited cross presentation of the extracellularly delivered antigen (54, 55, 62, 64, 65). Interestingly, LAIV is an intermediate between these two extremes. As an attenuated virus, LAIV results in activation of the innate immune system (56, 66-70) with stronger CD4 and CD8 T cell responses (55, 62, 71), but the more limited viral replication results in a decreased antigenic load.

Previous research has shown that the persistence, nature, and intensity of anti-influenza memory depend on the context of antigenic stimulation (72). Additionally, data we have generated in mice (Figure 1) and human subjects (Figure 2) suggests that previous influenza exposures shape the development of immunity on challenge with a drifted or shifted influenza strain. Given the profound differences in antigenic context between natural infection, IIV and LAIV, we will investigate how these different routes of early childhood exposure to influenza affect the functional potential of the anti-influenza immune response and determine the consequences this has on subsequent influenza vaccination. This improved knowledge of how early childhood influenza vaccination shapes the establishment of anti-influenza immunologic memory will enable both optimization of current influenza vaccination strategies and development of novel vaccines able to provide highly efficacious universal protection against both seasonal and potentially pandemic influenza strains.

2. STUDY DESIGN:

2.1: Overview:

This study will be conducted as a single center, prospective, open-label evaluation of different methods of priming on the anti-influenza CD4 T cell and antibody response in young children. It is anticipated that this study will last 3 years, with approximately 1 year of follow up for each subject. The study objectives are to evaluate the specificity and functional potential of the CD4 T cell response and the quantity, breadth and avidity of the neutralizing antibody response following either influenza infection or receipt of different types of licensed influenza vaccine as follows:

- Primary objective: To comprehensively evaluate the specificity and functional potential of CD4 T cell responses on a single cell level using intracellular cytokine staining following restimulation with pools of HA and NP peptides

Secondary objectives will include:

- To assess the full spectrum of antigen-specific CD4 T cell cytokine and chemokine production using multiplex cytokine assays
- To perform in depth characterization of the specificity of the CD4 T cell response following influenza vaccination or infection by Elispot assay
- To evaluate the humoral immune response that develops in response to infection or administration of the LAIV or IIV vaccines
- To determine the frequency of HA-specific memory B cells established using these priming conditions
- To determine the influence of the CD4 T cell response on the breadth and avidity of the post-vaccination antibody response using arrayed imaging reflectometry to rapidly quantify antibody levels against multiple HA proteins, microneutralization assays to quantify neutralizing antibody titers against different viral strains, and enzyme linked immunosorbent assays to determine HA antibody avidity and quantify stalk reactive antibody

[figure not shown]

Figure 2: Expansion of CD4 T cells directed against conserved peptides is seen following pandemic H1N1 vaccination, with a correlation between the development of an HA-specific CD4 T cell response and neutralizing antibody titer. Subjects received the monovalent inactivated subvirion A/California/07/09 vaccine and CD4 T cell responses against conserved and nonconserved peptide pools were examined by IFN γ Elispot assay using CD8 and CD56 depleted PBMCs. While a response to HA (A) and NP/M1 (B) peptide pools expected to be conserved compared to recently circulating H1N1 strains was detected, little response to peptides expected to be unique to this virus was seen in subjects without prior immunity (C). Error bars represent the standard error of the mean and P-values calculated using Wilcoxon signed rank test. Development of a CD4 T cell response was correlated with the maximum microneutralization titer achieved (D). R- and p-values determined using the Spearman correlation coefficient.

- To evaluate in an unbiased way the influence of previous influenza exposure on PBMC gene expression patterns using RNA-seq analysis
- To assess the mucosal immunity established by these modes of priming and determine whether any initially established differences in mucosal immunity are maintained on subsequent rechallenge with IIV

To accomplish these objectives, we plan to enroll a cohort of 60 children who have previously been vaccinated with at least 2 doses of IIV and who are between the ages of 24 and 35 months into cohort 1. These children will be block randomized to receive either LAIV (n=30) or IIV (n=30) in groups of 5 unless a history of isolated wheezing in the past year is present. As LAIV is not indicated in children with a history of recent wheezing, otherwise eligible children who have a history of wheezing will be defaulted to receive IIV. Children will have a blood draw and nasal wash on study entry and again at days 10 (+ 4 days/- 2 days) and 24 (+/- 4 days) post vaccination. They will then be followed through to the subsequent influenza season, when they will be rechallenged with IIV with blood draws and nasal washes pre-vaccination and again at days 10 (+ 4 days/- 2 days) and 24 (+/- 4 days) post vaccination (Figure 3).

The second cohort of children will be infants between 3 and 12 months of age who will be enrolled to investigate how the primary CD4 T cell response that develops following IIV administration differs from that established after natural influenza infection. Infants who receive vaccine in this cohort will be at least 6 months of age and will be enrolled in the fall before influenza begins to circulate in the community. Infants between 3 and 12 months of age who contract a natural influenza infection before any doses of vaccine are administered will be eligible for the natural infection arm of this cohort. Both of these infant groups will have blood drawn and a nasal wash obtained on study entry and at days 10 (+ 4d/- 2d) and 24 (+/- 4d) post-vaccination and then will be followed to the subsequent influenza season and rechallenged with IIV, with blood draws and nasal washes again completed pre-vaccination and at days 10 (+ 4d/- 2d) and 24 (+/- 4d) post-vaccination (Figure 3). Children who test positive for influenza will be allowed treatment with oseltamivir as recommended by the CDC (73). To accomplish this, the rapid influenza test result will be provided to the child's pediatrician, who will then coordinate treatment of the child.

Figure 3

[figure not shown]

Figure 3: Experimental schematic to determine whether the method of initial priming differentially poises subjects to respond to future influenza encounters. Subjects that receive LAIV, IIV, or that are naturally infected with influenza will have CD4 T cell and antibody responses examined at enrollment and at days 10 and 24 post vaccination. Cohort 1 contains children approximately 24-36 months of age. Cohort 2A contains infants 6-12 months of age in their first influenza season, while cohort 2B contains infants 3-12 months of age. All enrolled subjects will be followed longitudinally for a year and then will be revaccinated with IIV. CD4 T cell responses, antibody response, and transcriptional profiles will be examined prior to revaccination and at days 10 and 24 post vaccination.

2.2: Rationale for Study Design:

The age range of the first cohort of children was chosen because children first become eligible to receive LAIV at the age of 24 months. Thus, the age range of 24 through 35 months will capture children receiving LAIV for the first time. A block randomization scheme will be used as there is a large population of children with a past history of isolated wheezing as a result of viral illnesses such as bronchiolitis that have been shown to respond

equivalently to influenza vaccine (59, 74, 75). We feel that including this population of children in the study will improve recruitment and allow for broader applicability of our study results, but as these subjects are not eligible to receive LAIV (17, 18), their inclusion also precludes a completely blinded randomization scheme. With block randomization, eligible subjects will be enrolled to receive either LAIV or IIV in groups of 5 unless a history of isolated wheezing in the past year is present, in which case they will be defaulted to receive IIV as long as no other exclusion criteria are present.

The age range of the second cohort was chosen to enroll infants in their first influenza season with no history of prior exposure to influenza virus. Thus, this cohort will allow examination of the true primary response to influenza infection or inactivated vaccination. Children between 6 and 12 months of age who have not previously had an influenza infection or vaccination will be eligible to participate in the vaccination group. All of these children will receive IIV, as LAIV is not approved for children this age. This cohort will receive a prime-boost vaccination series, with vaccine doses separated by 28 (+ 14) days as recommended by the AAP and ACIP (17, 18). To minimize blood draws, we will only interrogate the immune response following the second vaccine dose. Children between 3 and 12 months of age who present with an influenza-like illness and have no previous history of influenza vaccination will be eligible to participate in the infection group. Study personnel will obtain nasal swabs from potential subjects for a rapid influenza antigen test on illness presentation (typically this occurs at day 3-4 post illness onset). If positive, they will be eligible for further study participation. Influenza real-time RT-PCR will be used to confirm rapid antigen test results, however these results will not be available in time to influence subject enrollment.

Blood draws will be obtained on study enrollment, day 10 (+ 4d/- 2d), and day 24 (+/- 4d) post enrollment as depicted in Figure 3. The blood draw on study enrollment will evaluate influenza-specific immunity at the time of study entry. The blood draw on day 10 (+ 4d/- 2d) post-vaccination will allow examination of each subject as CD4 T cell responses are peaking, while the blood draw at day 24 (+/- 4d) will capture the peak of the neutralizing antibody response and allow us to examine CD4 T cell responses as they contract. All subjects will be followed through to the subsequent influenza season, at which point they will be rechallenged with IIV. Blood draws will again be obtained pre-vaccination and at days 10 (+ 4d/- 2d) and 24 (+/- 4d) post vaccine administration, with the pre-vaccination blood draw providing a method to assess for undocumented influenza infection over the prior year. Blood draw volume will be determined based on subject weight, with a maximum of 1 mL/kg of blood obtained on any single draw and 3 mL/kg of blood over a 3 month period (see Table 1). At a minimum, 4 million PBMCs will be needed for flow cytometry and 3.6 million PBMCs will be needed for multiplex immunoassays. Assuming blood cellularity allows for recovery of an average of 1.5 million PBMC/mL, obtaining 5 mL of blood per draw will provide approximately 7.5 million PBMCs, which is just under the minimum amount of blood needed for these two assays alone. When a child's weight allows, a greater blood volume will be obtained to a max of 16 mL of blood per draw to provide for the additional cells needed to examine CD4 T cell specificity by Elispot assay (approximately 12 million cells), memory B cell responses (approximately 4 million cells), completion of gene expression studies, and allow for additional restimulation conditions to be tested using ICS and multiplex immunoassay as possible.

TABLE 1. BLOOD VOLUMES (mL) IN CHILDREN

Study Year 1					Study Year 2				mL/kg per draw	Max % of TBV (over 8 weeks)
Body Weight (kg)	Blood volume visit 1 (mL)	Blood volume visit 2 (mL)	Blood volume visit 3 (mL)	Max/8 weeks (mL)	Blood Volume Visit 4 (mL)	Blood Volume Visit 5 (mL)	Blood Volume Visit 6 (mL)	Max/8 weeks (mL)		
2-4	2	2	2	6	2	2	2	6	1	3.75%
5-10	4	4	4	12	4	4	4	12	0.8	3%
11-15	8	8	8	24	8	8	8	24	0.73	2.7%
16-20	12	12	12	36	12	12	12	36	0.75	2.8%
>20	16	16	16	48	16	16	16	48	0.76	2.8%

2.3: Rationale for Dosage:

All influenza vaccines will be administered at the age-appropriate recommended dosages as follows:

- IIV: Fluzone (Sanofi Pasteur, Swiftwater, PA) 0.25 mL administered intramuscularly to children between 6 and 35 months of age

- Children in cohort 2 (6-12 months of age) who are receiving influenza vaccine for the first time will receive 2 doses separated by 28 (+14) days
- LAIV: Flumist Quadrivalent (MedImmune) 0.2 mL administered intranasally

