13. DATA ANALYSIS AND MONITORING

13.1: Sample Size Determination:

	d=0.3	d=0.35	d=0.4
n1=25, n2=25	0.738	0.858	0.934
n1=30, n2=30	0.815	0.915	0.968
n1=35, n2=35	0.871	0.95	0.985
n1=30, n2=10	0.517	0.646	0.761
n1=30, n2=15	0.64	0.772	0.871
n1=30, n2=20	0.721	0.844	0.924

The primary endpoint of this study is CD4 T cell responses. Based on a study of immune response in children and adults (62), the overall mean percentage of IFN γ + CD4 T cells in 5-9 year old children vaccinated with IIV or LAIV is around 0.1%, or -3 in log₁₀ scale. The standard deviation (STD) in log₁₀ scale is around 0.4. The geometric mean differences induced by vaccinations or between the two types of vaccination is around 0.3 in log₁₀ scale. The above table summarizes statistical power based on Student's two sample *t*-test. Assuming our responses are similar, recruiting n=30 subjects in each group will give us adequate power (0.815) for Aim 1. Because LAIV is an attenuated virus, it is reasonable to assume that the difference in CD4 T cell responses induced by IIV and natural influenza infection is larger (d=0.4), therefore recruiting

n=30 subjects in the IIV group and n=15 subjects in the infection group can achieve adequate power (0.871) for Aim 2. For Aim 3, assuming that within-group STD is 0.4 and between-group STD is just 0.2, the power is 0.851 if we recruit n=105 subjects divided them into four subgroups (n1=30, n2=30, n3=30, n4=15).

13.2: Planned Statistical Analysis:

We outline the statistical analysis strategies for the specific aims as follows. **Aim 1:** A cohort of n=60 healthy children will be recruited and divided into two groups with equal sample size (n=30); one group will be vaccinated with LAIV and the other with IIV. Their T cell and antibody responses will be measured at three time points: Baseline, day 10, and day 24 post-vaccination. We will apply Shapiro-Wilk's test to check the normality. If the data passes the normality test, two sample *t*-tests will be used to detect significant mean difference between the two groups at each time point. Otherwise, Wilcoxon rank-sum test will be used. Because multiple response variables are used in this analysis, the *p*-values will be adjusted by the Benjamini-Hochberg multiple testing procedure (80) to control the false discovery rate (FDR) at the level of 0.05. In addition to pairwise comparisons, the following linear mixed effect model will be used to analyze data collected from all time points:

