$$y_{kit} = \alpha_k + \beta_k G(i) + \gamma_{kt} + \delta_{kit}. \quad (0.1)$$

Here y_{kit} represents the k th response variable measured from the i th subject at the t th time point; α_k is the overall mean value of y_{kit} ; $G(i)$ is a binary variable which equals 0 if the i th subject is vaccinated with LAIV and 1 otherwise; β_k is a linear coefficient that quantifies the magnitude of the group-effect; γ_{kt} is a random effect term that quantifies the time effects; and δ_{kit} represents independent measurement errors. Likelihood ratio test will be used to test $H_0: \beta_k = 0$ against $H_1: \beta_k \neq 0$. **Aim 2:** Two groups of infants will be recruited for this aim. The first group (n=30) will receive a prime-boost IIV series; the other group (n=15) consists of infants who are infected by influenza naturally. Multiple clinical endpoints will be recorded at 3 time points for both groups. We will apply two sample *t*-test (or Wilcoxon rank-sum test, if Shapiro-Wilks test rejects the assumption of normality) at each time point to detect significant group differences. In addition, we will apply a linear mixed effect model similar to Equation (1.1) to detect the overall group effect. The resulting *p*-values will be properly adjusted to control for FDR at a 0.05 level. **Aim 3:** All subjects (four subgroups; n=105) will be followed longitudinally for a year and then be revaccinated with IIV. CD4 T cell responses, antibody responses, and transcriptional profile (high-throughput RNA-seq) will be measured at three time points: prior to IIV re-vaccination, d10 and 24 days post re-vaccination. We will apply one-way ANOVA *F*-test (or Kruskal-Wallis test, if the normality assumption is rejected) to detect significant group differences at each time point. Post-hoc analysis based on Tukey's adjustment will be used to test for significant differences between groups. We will also apply a linear mixed effect model similar to Equation (1.1) to detect the overall group effect. For high-throughput transcriptional data, first we will apply suitable pre-processing techniques such as non-specific filtering (81), normalization (82) and batch-effect removing

(83). We then select differentially expressed genes at each time point by specialized procedures such as DEseq (84) and DEGseq (85). Benjamini-Hochberg procedure will be used to control FDR at a 0.05 level for all analyses.

13.3: Data and Safety Monitoring:

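### The plan asks whether year 1 group differences are maintained after rechallenge, but no planned analysis estimates how a group difference changes between years

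*Combined protocol and SAP*

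**What the plan says.** Section 1.1 sets the aim to "determine whether any initially established differences in mucosal immunity are maintained on subsequent challenge with IIV", and section 2.1 repeats it as a secondary objective, to "determine whether any initially established differences in mucosal immunity are maintained on subsequent rechallenge with IIV". Nasal washes are scheduled at all six visits, three in each year.

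Section 13.2 then gives:

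- **Year 1 (Aims 1 and 2).** Two-sample t-tests or Wilcoxon tests; for Aim 1 these "will be used to detect significant mean difference between the two groups at each time point". Aim 1 p-values go through the "Benjamini-Hochberg multiple testing procedure (80) to control the false discovery rate (FDR) at the level of 0.05", and Aim 2 p-values are also FDR-adjusted at 0.05.
- **Year 2 (Aim 3).** Responses "will be measured at three time points: prior to IIV re-vaccination, d10 and 24 days post re-vaccination". Groups are compared at each visit by four-group ANOVA or Kruskal-Wallis, and "Post-hoc analysis based on Tukey's adjustment will be used to test for significant differences between groups". The section closes with "Benjamini-Hochberg procedure will be used to control FDR at a 0.05 level for all analyses".
- **Mixed model.** The Aim 1 equation has one group coefficient per response variable, a time effect and an error term. For Aim 3: "We will also apply a linear mixed effect model similar to Equation (1.1) to detect the overall group effect".

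Aim 3 names CD4, antibody and transcriptional outcomes. Section 13.2 names no mucosal readout.

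**The concern.** To say that a difference was maintained is to compare two differences: the one in year 1 and the one in year 2. Section 13.2 has no year term, no group-by-year term, no change score and no interval or margin for the change. Even if the mixed model were run on both years together, its single group coefficient could not show a difference shrinking or growing. The only cross-year comparison, in section 5.5, flags individual children with a probable undocumented infection; it does not compare groups.

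That leaves the analyst with two sets of p-values. The natural temptation is to read significant in year 1 and non-significant in year 2 as a difference that was lost. At these sample sizes a non-significant year 2 test cannot show that the groups have converged. The year 2 pairwise comparison also carries a Tukey adjustment over four groups that the year 1 two-group tests do not.

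**Working it through.** **Inputs from section 13.1.** SD 0.4 log10; LAIV v IIV 30 v 30 with difference 0.3; IIV v infection 30 v 15 with difference 0.4; four groups of 30, 30, 30 and 15 (N = 105). SD and differences are planning values for blood IFNγ+ CD4 T cells; none are given for nasal wash readouts.

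**Assumptions.** Normal responses; two-sided 0.05; the same true difference in both years; within-child year-to-year correlation ρ from 0 to 0.6; no FDR step and no dropout.

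**1. Reproduce the plan.** Noncentral t with ncp = d / (SD·√(1/n1 + 1/n2)).

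- 30 v 30: 0.3 / (0.4·√(2/30)) = 0.3 / 0.1033 = 2.90; 58 df, critical t 2.00; power 0.815.
- 30 v 15: 0.4 / (0.4·√(1/30 + 1/15)) = 0.4 / 0.1265 = 3.16; 43 df, critical t 2.02; power 0.871.

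Both match section 13.1, and the method returns all 18 cells of its table.

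**2. Same difference in year 2 under Tukey.** Four groups and 105 − 4 = 101 error df give critical t 2.61, a per-pair alpha of 0.0104.

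| Pair | Smallest significant difference, year 1 | Year 2 Tukey | Power, year 1 | Year 2 Tukey |
|---|---|---|---|---|
| 30 v 30, 0.3 | 2.00 × 0.1033 = 0.207 | 2.61 × 0.1033 = 0.270 | 0.815 | 0.616 |
| 30 v 15, 0.4 | 2.02 × 0.1265 = 0.255 | 2.61 × 0.1265 = 0.330 | 0.871 | 0.708 |

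**3. Unchanged difference: chance of non-significance in year 2, given significance in year 1.** Simulation with at least 40,000 trials per setting; runs agree to about one percentage point.

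| Pair | Year 2 test | ρ = 0 | ρ = 0.3 | ρ = 0.6 |
|---|---|---|---|---|
| 30 v 30, 0.3 | Tukey | 38% | 35% | 30-31% |
| 30 v 15, 0.4 | Tukey | 29-30% | 27% | 23% |
| 30 v 30, 0.3 | plain t | 18-19% | 16% | 12% |
| 30 v 15, 0.4 | plain t | 13% | 11% | 9% |

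The plain-t rows show that part of this is ordinary limited power, which would remain if Tukey were dropped.

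**4. Direct contrast.** The SD of a child's change is 0.4·√(2(1 − ρ)), and the 95% CI half-width is t × that SD × √(1/n1 + 1/n2).

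- 30 v 30: ρ = 0 gives 2.00 × 0.566 × 0.258 = 0.29; ρ = 0.6 gives 2.00 × 0.358 × 0.258 = 0.18.
- 30 v 15: 0.36 and 0.23.

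With an unchanged difference, this contrast wrongly signals a fall in about 2.5% of trials, or about 3% of those significant in year 1.

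**The case against.** **No stated rule.** Nothing in section 13.2 says that a non-significant year 2 test means a difference was lost. A reader might infer that the trial will report persisting differences as lost; the documents do not support that. The objective could also be read as asking whether the groups still differ after rechallenge, which the year 2 comparison addresses and which suits hypothesis 3 in section 1.1. This stands as a limit on the claim. It does not supply an estimate of the change, and the objective's wording refers back to differences established initially.

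**FDR applies in both years.** A reader might infer that only the year 2 threshold is tightened. Benjamini-Hochberg also applies in year 1, so 2.00 and 2.02 are not the plan's full thresholds, and how Tukey and FDR combine in year 2 is not specified. The extra Tukey step is real; its net effect under the full plan was not computed.

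**No mucosal readout.** Section 5.2 stores nasal wash fluid and freezes the cells, section 5.3 defines no immune assay on them, and 13.2 lists no mucosal outcome. Applying the 13.2 tests here is an assumption, and the percentages borrow a blood CD4 SD. This stands.

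**Effect size.** Much larger miss rates appear if one assumes a 0.5-SD difference, but the protocol's planning values are 0.75 and 1.0 SD, so those rates should not be taken as the size of the problem.

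**Scope.** No CD4 or antibody objective speaks of differences being maintained. The point reaches those outcomes only if such a statement is made.

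**Conclusion.** The gap holds: a secondary objective that spans both years has no planned analysis that spans both years. The risk of a wrong reading is conditional on significance being compared across years. If it is, about 31-38% (30 v 30, 0.3 log10) or 23-30% (30 v 15, 0.4 log10) of unchanged differences found in year 1 would be non-significant in year 2, and 12-19% or 9-13% even without Tukey, for ρ from 0.6 to 0. FDR adjustment and dropout are not modelled. The plan should be changed, because the remedy is cheap and answers the stated question directly. It concerns a secondary objective and does not touch the Aim 1 and Aim 2 comparisons.

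**What to change.** Name the nasal wash response variable or variables, then add to section 13.2, for the mucosal objective and for any statement that a year 1 CD4 or antibody difference persisted or was lost:

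> For each within-cohort pair (LAIV v IIV; 2A v 2B), the change in the group difference from year 1 to year 2 at the matched post-exposure visits (day 10 and day 24; day 0 excluded) will be estimated on the log10 scale with a 95% CI, from a group-by-year term with child as random effect. Complete loss means a change equal and opposite to the estimated year 1 difference. A difference will be called reduced only if the CI lies wholly on the side of a smaller difference in year 2. A CI wholly on the other side will be reported as an increase. A CI that includes no change but excludes complete loss will be reported as no evidence of loss. A CI that includes both will be reported as inconclusive. A non-significant year 2 group test will not be read as loss.

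Day 0 is excluded because in cohort 1 the year 1 sample precedes the study vaccine, and in cohort 2B it is taken during acute illness. Table 2 heads visits 5 and 6 as days 7 and 21, whereas sections 2.1 and 5.1 give days 10 and 24; these must be reconciled before visits are matched.

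**Cost.** SAP wording and one more model per readout, with no change to visits, samples or enrolment. Some results will be inconclusive. Power to detect complete loss is 0.52-0.89 (30 v 30, 0.3 log10) and 0.59-0.93 (30 v 15, 0.4 log10) for ρ from 0 to 0.6. For a 0.5-SD difference it falls to 0.27-0.57 and 0.19-0.41.
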